16. PRIVACY AND CONFIDENTIALITY CONSIDERATIONS INCLUDING DATA ACCESS AND MANAGEMENT

As stated above in Section 11, 3 methods will be used for patient recruitment. First, a clinician may ask patients directly if they are interested in the study. UCSD Center for Pain Medicine clinicians can provide interested patients with an informational sheet about the study, including research staff contact information (Appendix 1). Second, a list of patients meeting specific 'International Statistical Classification of Diseases and Related Health Problems' (ICD-9 724.2) criteria for chronic low back pain will be sent an informational letter informing them about the study and inviting them to contact research staff if interested in learning more information (Appendix 1). Third, newspaper advertisements may be used (Appendix 2). All recruitment methods will rely on potential subjects voluntarily initiating contact with study research staff, an "opt-in" approach.

Once protected health information (PHI) is obtained, measures to protect privacy and confidentiality will be implemented. This will include coding, removal of identifying information, limiting access to data, and the use of a Certificates of Confidentiality that will be applied for from the National Institute of Drug Abuse following IRB approval. Physical safeguards for research data will include storage of paper records in locked files, separation of personal identifiable demographics data from study data referenced only to a unique study ID. Electronic records will be maintained on a HIPAA Compliant server using password protection.

All laboratory specimens, evaluation forms, reports and other records will be identified only by a coded number in order to maintain confidentiality. All records will be kept in a locked file cabinet. All computer entry and networking programs will be done with coded numbers only. All stored samples are accessible only to the HNRP laboratory personnel and the appropriate study members. Samples are stored under the coded identifiers in freezers equipped with locks, behind locked doors requiring ID scan entry.

The consent process will be performed under conditions to insure privacy and confidentiality. It will take place in a private exam room in the Department of Psychiatry, [name]. Should interviewee disclose suicidal ideation (Appendix 18), further evaluation will take place. Important elements of the history that permit appraisal of the seriousness of suicidal ideation include the intent, plan, and means; the availability of social support; previous suicide attempts; and the presence of comorbid psychiatric illness or substance abuse. After intent has been established, outpatient management will be sought.

17. POTENTIAL BENEFITS

There is no direct benefit to subjects.

18. RISK/BENEFIT RATIO

There is a substantial disconnect between the therapeutic use of cannabis and research on the risks and benefits of this practice. Although edible marijuana merchandise has become widely available at medical dispensaries, there is little information in the literature on the medical efficacy of these products ⁶². Pharmacologic oral preparations, which like the edible products, avoid deleterious effects upon the respiratory system, have had more attention from the scientific community ⁶³⁻⁶⁹. However, some experts have opined that whole plant cannabis is superior to the FDA approved oral cannabinoid preparations, e.g., synthetic tetrahydrocannabinol (dronabinol, Marinol®) and/or the synthetic analog of Δ9-THC (nabilone, Cesamet®). As testament to this belief, oral cannabinoids have been on the market in the United States for many years and are not widely used ⁷⁰. Peak plasma concentrations occur 1 to 6 hours after ingestion, with a magnitude approximately 10% of that achieved with smoking ⁷¹. As a result of the pharmacokinetics of oral preparations, it has been postulated that the preference expressed by patients for herbal cannabis is a result of the faster onset and shorter duration of action allowing titration of dose to the desired effect ⁷². The present study will compare the risk benefit ratio of herbal cannabis to an oral preparation (dronabinol). We know that cannabinoids appear to have some benefit in alleviating a heterogeneous collection of neuropathic pain conditions ^{2, 3}. Preliminary recommendations have been issued from the College of Family Physicians in Canada to help guide clinicians in prescribing cannabis for the treatment of for chronic noncancer pain ⁷³. But we do not know if chronic low back pain will respond to cannabis (or dronabinol).

19. EXPENSE TO PARTICIPANT

There will no expense for participants other than the cost of travel/parking.

20. COMPENSATION FOR PARTICIPATION

Subject payments are requested in order to compensate subjects for their participation. Total compensation could equal \$960.

Participants will be asked to arrange for transportation to and from the research site. For the screening appointment, participants will receive \$40. For the baseline visit, participants will be given \$10 for their arrival. Participants will receive \$20 for each microbiome stool and saliva sample. If participants provide stool and saliva samples for the first, second, and sixth experimental visits, they will receive \$60. Participants will receive \$20 for each microbiome blood sample. If participants provide blood samples for the first, second, and sixth experimental visits, they will receive \$60. We will budget \$20 per week x10 weeks equals \$200 and \$65 per visit x6 visits equals \$390. The total per subject payment will be \$760 for visits. Compensation will be pro-rated if the subject does not complete by weeks of participation and study visits attended.

For the baseline driving visit, participants will receive \$20. In addition, we will pay subjects for one other driving session. In this driving session, we are budgeting \$20 per hour for 9 hours equals \$180 per subject. While the experiment will last 8 hours, the time for preparation and lunch will have the participant stay at our center for a total of 9 hours. Compensation will be pro-rated if the subject does not complete driving simulation at \$20 per hour. The total compensation for both driving visits will be \$200.

Inasmuch as participants will be given a vaporizer worth \$600 to take home and use, they will not be compensated for their visits and weekly journals until study completion and after they return the vaporizer. Should they withdraw from the study prematurely, they will be compensated for completed visits but still be required to return the vaporizer they were given in order to be compensated.

22. FUNDING SUPPORT FOR THIS STUDY

This study will be funded by the National Institute of Drug Abuse as 1R01DA038634-01A1 "A Randomized, Cross-Over Controlled Trial of Dronabinol and Vaporized Cannabis in Neuropathic Low Back Pain"

23. BIOLOGICAL MATERIALS TRANSFER AGREEMENT

N/A

24. INVESTIGATIONAL DRUG FACT SHEET AND IND/IDE HOLDER

IND 102847 Vaporized Cannabis

This study involves an FDA-regulated investigation product for vaporized cannabis. [name] is the IND holder (subsequently transferred to [name]). The IND Acknowledgement and Form 1572 from 2008 are attached (Appendices 20 and 21). An email from the FDA official is attached stating that the IND is may be used for the present study (Appendix 22).

The investigational drug will be handled by the UCSD Investigational Pharmacy. Accountability records will be maintained according to policies and procedures (Appendix 23). This has been discussed with the UCSD Investigational Pharmacy. Sign out logs will be kept as dictated by NIDA and DEA officials. At the end of each experimental session and/or study visit, all unused materials will be collected and stored in a sealed container that will be returned to the UCSD Investigational Pharmacy, with the exact amount noted and dated in the log (e.g., "bulk cannabis weighing x mg"). All records will be made available to the DEA and the Research Advisory Panel of California, which supervises all controlled substance research in California. At the end of the study, all unused plant

material (i.e., cannabis not vaporized or the debris from vaporization) from each subject's 8 week treatment period and, if applicable, driving simulation session will be collected and placed in a container, which will be disposed at the facility used to incinerate unwanted medical or containment materials.

25. OTHER APPROVALS/REGULATED MATERIALS

No other UCSD review committees have reviewed and approved/authorized this study or are currently reviewing the study. However, we have multiple federal and state reviews that are being conducted. Marijuana is currently classified at the highest (most restrictive) level as a Schedule I drug (no accepted medical use, high potential for abuse). U.S. investigators are subject to specific Food and Drug Administration (FDA) and Drug Enforcement Agency (DEA) regulations concerning research with controlled substances. These reviews are described below:

DEA: Under the Controlled Substances Act (21 USC 822 (a)(1)) and implementing DEA regulations, persons conducting clinical research with any controlled substance must register with the DEA, keep specific types of records, provide evidence of safety precautions to prevent diversion, and periodically report to the DEA. The PI, [name], has maintained a Schedule I license to study marijuana for over a decade. The DEA in Washington is awaiting UCSD IRB approval and will then have the San Diego Branch inspect the UCSD Investigational Pharmacy to insure that the facility meets their guidelines for secure handling of cannabis.

FDA: [name], has an IND to study vaporized cannabis. A document was made to them earlier this year providing the background on the present proposal.

NIDA: The source of marijuana will be the National Institute on Drug Abuse (NIDA); they will not release the marijuana until DEA and FDA approvals are granted. As we have documentation that the FDA will allow us to proceed (Appendix 21), the only remaining regulatory approval is that from the DEA.

A Certificate of Confidentiality has been obtained from NIDA.

Research Advisory Panel of California: Some States may have their own registration requirements for Schedule I substances above and beyond the Federal requirements. California requires registration with the Regulatory Advisory Panel of California (RAPC). We have received approval from this agency (Appendices 24 and 25).

30. PROCEDURES FOR SURROGATE CONSENT AND/OR DECISIONAL CAPACITY ASSESSMENT

N/A

Dronabinol and Vaporized Cannabis in Chronic Low Back Pain

Statistical analysis plan

Principal investigators:

**[name].
[name]. (retired)**

Protocol Statisticians:

**[name].
[name].**

April 24, 2020

1. Summary of Study Design

This study is a prospective, randomized, placebo controlled, double blind, phase 2/3 clinical trial of dronabinol and vaporized cannabis for the treatment of chronic low back pain. A total of 120 (n = 120) subjects with chronic low back pain, aged between 19-70 years will be randomized in a ratio of 1:1:1 to the three treatment arms (40 participants per arm): 1) vaporized 3.7% Δ9-THC /5.6% cannabidiol plus placebo oral pills, 2) oral Δ9-THC (dronabinol) plus vaporized placebo, and 3) double placebo. The three arms are shortly called 1) vaporized cannabis; 2) dronabinol; 3) placebo. After randomization, each patient will receive study medication at home for 8 weeks after which they will be tapered off of investigational treatments over two weeks. The three study periods include: i) Titration (weeks 0-4); ii) Treatment (weeks 5-8); iii) Tapering (Weeks 9-10). During the titration period, patients will undergo titration of vaporized medication from 4 puffs to 18 puffs, or oral medication from 5 mg qd to 10 mg tid per day. Subjects will be dropped from the study by the end of Week 4 if they are unable to tolerate the minimum amounts of medication described above, and replaced by another volunteer. During the treatment period, subjects will be expected to consume the amount of study medication that they titrated themselves up to by the end of week 4. During the tapering period, patients will slowly withdraw from medication over two weeks. During treatment at home (weeks 1-8), patients will maintain a paper daily diary to record their intake of study medications, and breakthrough pain medications, as well as pain relief measurements. Outcome measure (such as self-report forms and neuropsychological testing) will be collected during the six study visits. If participating in Driving Simulation, subjects with driver licenses will be scheduled for two experimental visits.

The variables being assessed include vital signs, pain evaluation (cold pressor test), driving simulation, iPad performance testing, blood draws, neuropsychological tests, self-reports (BDI-II, Neuropathic Pain Scale, side effects). The primary outcome will be measured using self-reported average numerical pain intensity during the past 24 hours. A secondary outcome measure will be the level of use of breakthrough pain medication, mood, attention, verbal learning, fine motor coordination, psychomimetic side-effects, and driving performances.

The three main objectives of this study are to 1) assess whether treatment with vaporized whole plant cannabis or oral Δ9-THC reduces spontaneous and evoked pain more than placebo, and whether there are differences between the two active treatments. 2) examine the effects of vaporized whole plant cannabis and oral Δ9-THC (dronabinol) on mood, neuropsychological function, and psychomimetic side-effects (high, stoned, etc.) compared to placebo and to each other. 3) examine the acute effects (after receiving stable treatment for 4 weeks) of vaporized whole

plant cannabis and oral Δ9-THC compared to placebo and each other on driving skills.

2. Baseline characteristics, treatment, and study enrollment summaries

2.1 Demographic and medical and laboratory characteristics

These measures will be tabulated and summarized by treatment arm using Mean (SD), N (%), and Median (IQR), as appropriate. Fisher's exact test for categorical variables and analysis of variance (ANOVA) for numeric variables will be used to test the overall differences between the three treatment arms.

2.2 Study enrollment, Randomization, and dropout

The 120 eligible participants will be randomized to Arm A (vaporized Δ9-THC (3.5%)/placebo oral pill, n=40), to Arm B (dronabinol/vaporized placebo THC, n=40), or Arm C (double placebo, n=40). With a 16% dropout rate, we expect 33 subjects completing the 8-week visit for each arm. The completers who have a valid driver's license will implement driving simulation. The number (%) of subjects randomized, number (%) of subjects completing the 8-week-treatment, and number (%) of patients lost to follow-up will be summarized overall and by treatment arm. Fisher's exact test will be used to compare the arms in the proportions of lost to follow-up. Reasons (if known) for lost to follow-up will also be recorded. The comparisons are following an order of importance: arm A vs. arm B; arm A vs. arm C; arm B vs. arm C. Since the three comparisons have different levels of importance, no correction will be done for multiple comparisons.

The dropouts and completers will be compared, overall and stratified by treatment arm, with respect to their baseline demographics, medical characteristics, and the prevalence and timing of adverse events. The statistical analysis will use Fisher's exact test for binary and nominal variables, Student's t test or Wilcoxon rank-sum test for continuous variables, and log-rank test for time-to-event analysis, censored at the time of dropout.

2.3 Treatment Adherence and Discontinuation

The number (%) of subjects who discontinue assigned study treatment permanently, dates and reasons for treatment discontinuation will be summarized overall and by treatment arm, and will be compared between arms using Fisher's exact test with the strategy of the comparison described in 2.2.

3. Safety and treatment toxicity

3.1 Adverse events

The number (%) of subjects with adverse events will be tabulated and summarized overall and by treatment arm, with the grade of the adverse event (1-4) included. The study week and reasons for adverse events will be included. Using the Kruskal-Wallis rank sum test, the number of adverse events per individual and maximal grade for each individual were compared among the three treatment arms. The proportion of participants with severe adverse events (leading to permanent treatment determination) will be compared between treatment arms with Fisher's exact test using the strategy of the comparison described in 2.2.

4. Endpoints

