15. RISK MANAGEMENT PROCEDURES AND ADEQUACY OF RESOURCES

At every study visit, stopping criteria will include:

Pulse: an irregular pulse or pulse rate > 110 beats per minute

Blood Pressure: systolic blood pressure > 180 mmHg or diastolic > 110 mmHg

Respirations: respiratory rate > 20 breaths per minute

Pulse: an irregular pulse or pulse rate greater than 110 beats per minute will result in cessation of participation and, if deemed advisable by a study clinician, transfer to the emergency department (across the street from our research center).

Blood Pressure: If the systolic blood pressure is ≥ 160 to < 180 mmHg or the diastolic is ≥ 100 to < 110 mmHg, a study clinician will conduct an evaluation to see if the participant has symptoms that would mandate discontinuation. Examples would include severe headache, confusion, chest pain, dyspnea, irregular heartbeat, and/or palpitations. Final determination regarding possible discontinuation will be made by a study investigator. If discontinued from the study, the participant will be asked to have their blood pressure evaluated by their primary care physician as soon as possible. If the systolic blood pressure is > 180 mmHg or the diastolic is > 110 mmHg, the participant will be discontinued from the study and either be transferred to the emergency department or be asked to visit their primary care physician as soon as possible. The end organ response to the blood pressure will guide the clinician's decision (e.g., the development of angina pectoris or hemiplegia will mandate transfer to the emergency department).

Respirations: shortness of breath will result in potential cessation of participation and possible transfer to the emergency department following evaluation by a study clinician, who will consult with the study investigator.

A locally developed self-report instrument, the Cannabis Solicited Adverse Events (Appendix 29) will be administered to assess distress from psychological effects of cannabis. This will be performed on a prn basis by the trained staff and routinely at the end of the acute

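### SAP 3.1 compares adverse event counts between arms without time on study, so unequal early stopping can understate the burden of the arm that stops more

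*SAP*

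**What the plan says.** **Between arms (SAP 3.1).** "The number (%) of subjects with adverse events will be tabulated and summarized overall and by treatment arm". On timing, the section adds only this: "The study week and reasons for adverse events will be included". The Kruskal-Wallis test is then applied as follows: "the number of adverse events per individual and maximal grade for each individual were compared among the three treatment arms". No person-time rate, exposure offset or between-arm time-to-event method is named. A further comparison, by Fisher's exact test, covers stopping: "The proportion of participants with severe adverse events (leading to permanent treatment determination) will be compared between treatment arms".

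**Dropouts versus completers (SAP 2.2).** The two groups are compared "with respect to their baseline demographics, medical characteristics, and the prevalence and timing of adverse events". Binary variables get Fisher's exact test. Timing gets a "log-rank test for time-to-event analysis, censored at the time of dropout".

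**Discontinuation (SAP 2.3).** Dates and reasons are summarised by arm, and arms are compared by Fisher's exact test.

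**Early exit.** Under Protocol section 9 and SAP section 1, people who cannot tolerate the minimum amounts by the end of Week 4 leave the study and are replaced. Under Protocol section 15, an irregular or fast pulse "will result in cessation of participation and, if deemed advisable by a study clinician, transfer to the emergency department", and Grade 2 or 3 AEs prompt a review of whether to discontinue.

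**After exit.** The protocol describes a taper of one to two weeks with telephone calls, and follow-up of AEs until they resolve. It does not describe collecting new AEs up to Week 8 in people who have left.

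**The concern.** A count of AEs, and the worst grade reached, can only grow with time observed. Someone who leaves in Week 2, even with a taper added, has far less time to report new events than someone who completes 8 weeks plus taper. Several of the exit routes are tied to tolerability, and one acts during the first four weeks. It is therefore plausible that the less well tolerated arm is also the arm observed for less time, which pulls its count down.

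The lay summary in the protocol gives assessment of risk and benefit as a purpose of the trial, so comparative tolerability matters. In SAP 2.2 the same mechanism affects crude AE prevalence: dropouts have less time at risk by definition.

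**Working it through.** **1. The plan's own figure.** The only stated figure that governs time on study is 16% dropout, leaving 33 completers per arm. 40 × (1 − 0.16) = 33.6, rounded down to 33. It reproduces. The SAP gives no dropout by arm, no AE rate and no power for AE comparisons; values below for these are assumptions.

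**2. Mean weeks at risk per person.** Formula: 8 × (1 − d) + t × d, where d is the dropout proportion and t the mean week of dropout. Taper weeks are left out.

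| Dropout | t = 4 | t = 2 |
|---|---|---|
| 5% | 7.80 | 7.70 |
| 10% | 7.60 | 7.40 |
| 16% | 7.36 | 7.04 |
| 30% | 6.80 | 6.20 |
| 40% | 6.40 | 5.60 |

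With 16% in every arm, time at risk is the same and the arm comparison is unbiased.

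**3. Count ratio at equal true rates.** The expected ratio is the ratio of weeks at risk. For 30% versus 10% with t = 2: 6.2 / 7.4 = 0.84. For 40% versus 5% with t = 2: 5.6 / 7.7 = 0.73.

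**4. What the test does, two arms.** Simulation with 40 per arm, Poisson AEs at 0.2 per week, and dropout uniform over weeks 0-4:

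| True rate ratio | Dropout | Count ratio | Kruskal-Wallis rejects | Rate test with exposure rejects |
|---|---|---|---|---|
| 1.0 | 30% vs 10% | 0.84 | 15% | 4% |
| 1.0 | 40% vs 5% | 0.73 | about 39% | about 5% |
| 1.5 | 30% vs 10% | 1.25 | about 15% | about 65% |
| 1.5 | 16% vs 16% | 1.50 | about 52% | about 65% |

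The third count ratio follows from step 3: 1.5 × 0.84 = 1.26.

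**5. Three arms, as planned.** At equal rates of 0.2 per week, Kruskal-Wallis rejects in 4% of runs with 16% dropout in each arm, in 9% with 30/16/5% dropout at mean week 4, and in 30% with 40/16/5% at mean week 2. In the last case the mean counts are 1.12, 1.41 and 1.54, while events per person-week are 0.20 in all three arms.

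**6. If the AE that causes stopping is counted.** Add one AE to every dropout. For 30% versus 10% at t = 2, the means are 0.2 × 6.2 + 0.30 = 1.54 and 0.2 × 7.4 + 0.10 = 1.58, a ratio of 0.97, and the two-arm test rejects in about 5% of runs. The three-arm 40/16/5% case also falls to 5%.

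**7. Dropouts versus completers.** 120 × 0.16 gives 19 dropouts and 101 completers. With the same constant hazard h for everyone, and dropout uniform over 8 weeks and unrelated to AEs, completer prevalence is 1 − exp(−8h) and dropout prevalence is 1 − (1 − exp(−8h)) / (8h).

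| h per week | Dropouts | Completers | Fisher rejects |
|---|---|---|---|
| 0.05 | 18% | 33% | about 20% |
| 0.1 | 31% | 55% | about 47% |
| 0.2 | 50% | 80% | about 70% |

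If half of dropout is AE-driven, prevalence becomes 57% vs 27%, 64% vs 51% and 74% vs 78%, and false rejections with dropouts lower fall to 0%, 0% and 5%. If all dropout is AE-driven, dropouts are at 100% against 20%, 47% and 76%, and Fisher's test points the right way.

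**The case against.** The strongest reply has four parts.

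- **The arm bias needs unequal dropout.** The documents give a single 16%, and the splits used here are assumed. This stands. A reader might infer that the planned test will make the worst tolerated arm look safer; the documents support only that it can.
- **Tolerability-driven stopping brings its own AE.** Counting that event nearly removes the distortion, as step 6 shows. This stands as to size. But in that case an arm with three times the dropout, all of it AE-related, shows no difference on the count. With a true background ratio of 1.5 the count test has 46% power against 85% for a rate test.
- **The plan has safeguards.** SAP 3.1 compares AEs leading to stopping, SAP 2.3 compares discontinuation, and SAP 2.2 compares loss to follow-up. These would expose an arm with many early stops. They do not correct the count or grade comparison.
- **SAP 2.2 already handles timing.** A reader might infer that the comparison of dropouts with completers ignores time on study, or will show the reverse of the truth. Neither is supported. A log-rank test censored at dropout is planned in the same paragraph, and the reversal occurs mainly when dropout is not AE-driven. That test is not a comparison between arms, however, so it does not repair SAP 3.1.

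**Conclusion.** The concern holds in a limited form. The count and maximal-grade comparisons in SAP 3.1 take no account of time on study, in a trial whose rules remove some poorly tolerating participants early. If dropout differs between arms, the count comparison can understate the burden of the arm with more early stopping. The illustrative size is a count ratio of about 0.84 and about 15% false rejection at 30% versus 10% early dropout. There is no bias at equal dropout, and little when each dropout's causal AE is counted. These figures rest on assumed AE rates, assumed dropout splits and a constant weekly hazard. No size was computed for maximal grade.

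Crude prevalence in SAP 2.2 can mislead when dropout is not mainly AE-driven, but the planned log-rank test already offers a sounder basis. It might also be inferred that maximal grade should be dropped. That is not justified: it carries the distinction between Grades 3 and 4, which time to first Grade 2 or higher AE would lose. This is an inexpensive improvement to a safety analysis and leaves the primary efficacy result untouched.

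**What to change.** **SAP 3.1.** Make the between-arm count comparison an AE rate per person-week, by negative binomial or Poisson regression with log time on study as offset. Add time to first Grade 2 or higher AE by arm. Keep raw counts, n (%) and maximal grade as descriptive tables. Keep the Fisher comparisons of AEs leading to stopping (SAP 3.1) and of discontinuation (SAP 2.3) as partial safeguards.

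**SAP 2.2.** Base the AE inference for dropouts versus completers on the planned log-rank test or on events per person-week. Report crude prevalence descriptively, without Fisher's test.

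**Definitions to add.** State when time on study ends for AE purposes (last dose, end of taper or last contact) and whether replaced participants stay in the AE tables; the documents do not say.

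**Cost.** SAP wording and a few modelling lines. AE study week and discontinuation dates are already to be reported. One limit: a single rate assumes a constant hazard. If AEs are three times as frequent in weeks 0-4, the 40/16/5% dropout case gives rates of 0.215, 0.205 and 0.201 for arms with identical hazards. That is a small lean the other way, which a term for study period would address.

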administration session. The items on this instrument ask participants about experiencing anxiety, paranoia, and hallucinations. Excess intoxication will also be assessed using this instrument which asks participants about their having dizziness, drowsiness, confusion, emotional changes, and/or cognitive changes. Positive responses to these items, if Grade 2, 3 or 4 (see below for definitions), will result in notification of a study clinician who will speak with the participant to see if discontinuation of participation in the study would be in her or his best interest.

Using the Cannabis Solicited Adverse Events instrument mentioned above, an Adverse Events Form (Appendix 30) will be completed. Adverse events will be characterized as 1 = Mild, 2 = Moderate, 3 = Severe, and 4 = Life Threatening using the following definitions (consistent with those used by the National Cancer Institute):

GRADE 1 MILD	GRADE 2 MODERATE	GRADE 3 SEVERE	GRADE 4 POTENTIALLY LIFE-THREATENING
Mild symptoms causing no or minimal interference with usual social & functional activities with intervention not indicated	Moderate symptoms causing greater than minimal interference with usual social & functional activities with intervention indicated	Severe symptoms causing inability to perform usual social & functional activities with intervention or hospitalization indicated	Potentially life-threatening symptoms causing inability to perform basic self-care functions with intervention indicated to prevent permanent impairment, persistent disability, or death

Inasmuch as the scoring of Grades 2, 3, and 4 mention that an intervention is indicated, AEs with Grades 2 or 3 will be brought to the attention of a study clinician so that s/he may interact with the participant to determine if discontinuation of study participation is warranted. This will be done in consultation with an investigator. Grade 4 AEs will be managed by reports tendered to the FDA and the IRB within the required time limits specified by each organization. There will also be a determination of whether the AE is related, possibly related or not related to the study by the investigator for Grades 1 to 4.

Furthermore, the participant will be followed by the research team to insure that the AE(s) resolve. This might include recommending that the participant see their primary care physician (e.g., for a change in blood pressure medication).

Risks will also be mitigated using the following measures:

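### SAP 3.1 ties its pairwise test of severe adverse events to the end of treatment, so Grade 3–4 events after which treatment continued appear to be left out

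*SAP*

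**What the plan says.** Protocol section 15 fixes the severity scale: "Adverse events will be characterized as 1 = Mild, 2 = Moderate, 3 = Severe, and 4 = Life Threatening". Its table describes Grade 3 as "Severe symptoms causing inability to perform usual social & functional activities with intervention or hospitalization indicated". The definition rests on function and need for care; whether study treatment goes on does not enter into it.

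The same section treats stopping as a separate, case-by-case decision: "AEs with Grades 2 or 3 will be brought to the attention of a study clinician", the purpose being "to determine if discontinuation of study participation is warranted". Some exits do not refer to grade at all, for example "an irregular pulse or pulse rate greater than 110 beats per minute will result in cessation of participation".

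SAP 3.1 plans three things for adverse events:

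- a table by arm, "with the grade of the adverse event (1-4) included";
- a Kruskal-Wallis analysis in which "the number of adverse events per individual and maximal grade for each individual were compared among the three treatment arms";
- a Fisher's exact test, of which it says: "The proportion of participants with severe adverse events (leading to permanent treatment determination) will be compared between treatment arms". This test follows the strategy of SAP 2.2, which is A vs B, then A vs C, then B vs C, without multiplicity correction.

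No grade threshold is given for the third item. SAP 2.3 separately compares permanent discontinuation of study treatment for any cause, with reasons summarised.

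**The concern.** The only pairwise test that carries the label 'severe' has a condition attached that the protocol's scale lacks. A reader of the results will take a proportion with severe adverse events to mean Grade 3 or higher on the protocol scale. Under the SAP sentence it would be something else: either stopping because of an adverse event, or the overlap of stopping and severity.

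This matters because Protocol section 5 sets out to weigh risk against benefit for the two active treatments. The vaporized cannabis versus dronabinol contrast, first in the SAP's order of importance, is the one for which a clear proportion with severe events would be most useful.

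**Working it through.** No figure in the plan is at issue: neither document gives an event rate, power or sample size for this test. The check is a comparison of event sets, followed by an illustration with assumed counts.

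**Step 1. Do the two sets differ under the protocol's own rules?** Yes, in both directions.

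- A Grade 2 event goes to a clinician who may decide on discontinuation, so an event below Grade 3 can end treatment.
- A Grade 3 event goes through the same case-by-case decision, so it need not end treatment. Nor does section 15 make discontinuation automatic at Grade 4: it speaks of regulatory reporting and, for the solicited-events instrument, of a clinician's conversation with the participant.
- Pulse and blood-pressure findings can end participation without reference to grade. (I assume that ending participation also ends study treatment, apart from the taper.)

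**Step 2. What does each reading count?** For one arm, let x = participants with a Grade 3–4 event who continued treatment, y = those with a Grade 3–4 event who stopped because of it, and w = those with only Grade 1–2 events who stopped because of one.

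| Event set | Count |
|---|---|
| Grade 3 or higher on the protocol scale | x + y |
| Parenthesis defines 'severe' | y + w |
| Parenthesis restricts 'severe' | y |

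The x participants are missing under both readings of the parenthesis. The w participants are added only under the definitional one.

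**Step 3. Assumed counts in an arm of 40** (SAP 5.1 gives 40 per arm).

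| x, y, w | Grade 3+ | Definition | Restriction |
|---|---|---|---|
| 1, 1, 4 | 2 (5.0%) | 5 (12.5%) | 1 (2.5%) |
| 3, 1, 4 | 4 (10.0%) | 5 (12.5%) | 1 (2.5%) |
| 2, 1, 2 | 3 (7.5%) | 3 (7.5%) | 1 (2.5%) |

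In the last row the first two counts agree, yet only one participant is common to both.

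**Step 4. Can this change the test?** For 0 of 40 against k of 40, the two-sided Fisher p-value is 2 × C(40,k) / C(80,k).

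- k = 5: 2 × 658,008 / 24,040,016 = 0.055
- k = 6: 2 × 3,838,380 / 300,500,200 = 0.026

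Suppose one arm has x = 1, y = 5, w = 0 and the comparator has no events. Grade 3 or higher is then 6 vs 0 (p = 0.026), while either reading of the SAP sentence gives 5 vs 0 (p = 0.055). The same happens one step up: 1 vs 7 gives 0.057 and 1 vs 8 gives 0.029. One participant can move the result across 0.05. The two-sided level is an assumption, since the SAP gives 5% without saying which.

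**Step 5. Do the other analyses supply the missing comparison?** The Kruskal-Wallis test ranks all grades across three arms at once; it yields neither a proportion with Grade 3 or higher events nor a contrast between two arms. The test in SAP 2.3 is pairwise but concerns stopping for any cause. Neither is a pairwise comparison of the proportion with protocol-severe events.

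**The case against.** The strongest reply is that this is a wording matter in a plan that already handles severity. Most of that reply stands as a limit on the point.

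- *Severity is otherwise untested.* A reader might infer this, and it would be wrong. The sentence before the Fisher test compares maximal grade across arms, where a Grade 3 or 4 event counts whether or not treatment continued. SAP 6.2 also marks severity grade for comparison between arms in the closed monitoring report.
- *The SAP contradicts the protocol's scale.* A reader might infer this too. It follows only if the parenthesis is a definition. Read as a restriction, it selects a subset of severe events, and no Grade 1–2 event is ever called severe. The syntax does not settle the matter, and 'discontinuation' is itself inferred from 'determination'.
- *The test counts the wrong events.* This goes too far. Adverse events that lead to discontinuation are a legitimate safety outcome; the difficulty is the label and the lack of a stated event set.
- *The parenthesis may be a loose gloss, with Grade 3 or higher intended.* That is possible, and then nothing need be left out. But the SAP states no threshold, so the numerator would be open to choice at analysis.

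What the reply does not remove is the omission: under either the definitional or the restrictive reading, Grade 3–4 events after which treatment continued do not enter the pairwise test.

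**Conclusion.** The point holds in limited form. The SAP's pairwise Fisher comparison labelled 'severe' carries a treatment-ending condition that the protocol's Grade 3 definition does not have. Taken as a definition or as a restriction, that condition drops Grade 3–4 events after which treatment continued; taken as a definition, it also admits Grade 1–2 events that ended treatment. As written, the plan leaves no pairwise comparison of the proportion with protocol-severe events.

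The effect is confined to one safety comparison. Efficacy analyses are untouched, and graded severity is still tabulated and tested across three arms. The size cannot be estimated from the documents; the counts used here are assumed and show only that a shift of one participant can matter with 40 per arm. The conclusion rests on reading 'determination' as termination or discontinuation. It should be settled before unblinding, since the choice of event set could otherwise follow the data.

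**What to change.** In SAP 3.1, replace the sentence on severe adverse events with two separately labelled outcomes, each compared by Fisher's exact test under the SAP 2.2 strategy:

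- (a) participants with at least one adverse event of Grade 3 or higher on the scale in Protocol section 15;
- (b) participants who permanently discontinued study treatment because of an adverse event, not described as severe.

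Keep the grade table and the Kruskal-Wallis analysis as they are. The cost is SAP wording and one extra table row. No new data are needed: grades are already planned in SAP 3.1 and discontinuation reasons in SAP 2.3. The change concerns the analysis definition only and leaves the rules for stopping treatment as they stand.
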